#### 6.2.3 Statistical model, assumptions and hypotheses

The following statistical analyses will be implemented for each cohort separately and pooled cohorts. For subjects who stopped the study drug intake due to Covid-19 and restarted drug intake after tested negative to Covid-19 (i.e. OTHER-5 and with PD identifier OTH36), their assessments after treatment discontinuation will not be consider.

For each secondary variable (apart from hematuria, Bb and C3 biomarker) a similar statistical model will be used as described for the primary variable in Section 6.1.3.

Additionally, for Cohort B only, the log ratio to baseline in UPCR and UACR derived from 24h urine collection will also be analyzed with the same MMRM model as in Section 6.1.3.

#### 6.2.3.1 Sensitivity analyses

Commercially Confidential Information

## 6.3 Exploratory objectives

6.3.1 Variables

## 6.3.2 Descriptive analyses

#### 7 Statistical methods for safety and tolerability data

All subjects within the Safety analysis set will be included in the safety data analysis.

#### 7.1 Variables

Novartis

Adverse events, vital signs (blood pressure, pulse rate, body temperature), ECG intervals, laboratory measurements, as well as subject demographics, baseline characteristics, and treatment information.

#### 7.2 **Descriptive analyses**

#### Subject demographics and other baseline characteristics

All data for background and demographic variables will be listed by treatment group and subject. Summary statistics will be provided by treatment group.

Relevant medical histories and current medical conditions at baseline will be summarized (separately) by system organ class and preferred term, for all subjects.

Relevant medical history, current medical conditions, results of laboratory screens, drug tests and any other relevant information will be listed by treatment group and subject.

#### Treatment

Data for study drug administration and concomitant therapies will be listed by treatment group and subject.

Data for study drug administration will be summarized by treatment group and will include number of subjects who took all the planned doses of LNP023.

Concomitant medications and significant non-drug therapies prior to and after the start of the study treatment will be listed and summarized according to the Anatomical Therapeutic Chemical (ATC) classification system, by preferred term and cohort group for all subjects.

In addition, the above two summary tables will be produces for the medications of interest listed below:

Concomitant medication is defined as any medication started on or after LNP023 treatment and ended/ongoing by Day 84. Prior medications are defined as any treatment started and ended before the first dose of LNP023 on Day 1.

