• A safety follow-up period of 12 weeks, without treatment, will follow. There will be 3 outpatient visits on Days 113, 127 and 155Commercially Confidential Information

An end-of-study (EOS) visit is scheduled on Day 183

Commercially Confidential Information

Patients will remain on their supportive therapy, i.e. ACEi and/or ARB or other antihypertensive therapy,

Commercially Confidential Information

for the duration of the trial. To be dosed, patients must have been on stable therapy with an ACEi and/or ARB,

Commercially Confidential Information

During the treatment period, no change in medication is allowed except for safety reasons.

Commercially Confidential Information

Patients must receive vaccinations against *N. meningitidis*, *S. pneumoniae* and *H. influenzae* prior to first LNP023 dosing. Commercially Confidential Information

Page 31 Protocol No. CLNP023X2202

Commercially Confidential Information

Efficacy in terms of proteinuria and individual clinical response to various pharmacodynamic markers as well as pharmacokinetics will be assessed over the 12 week treatment period (refer to Table 8-1 and Table 8-2 the assessment schedule for detailed sampling time).

In this context, proteinuria will be assessed by collecting 24-h urine and first morning void urine to assess the change in and evolution of: UA and UP excretion, UACR and UPCR, creatinine clearance and hematuria.

Commercially Confidential Information

Safety monitoring includes the following assessments for each visit during Treatment period CCI and alerts will be set up for abnormal values to be reported immediately to Investigator and Sponsor:

- Renal function surveillance including serum creatinine, eGFR (using the CKD-EPI formula), hematuria, UA, UACR and UPCR assessments (refer to Section 8.3)
- Blood pressure (refer to Section 8.4.4.2)

Commercially Confidential Information

- 12-lead ECG (PR interval, QRS duration, heart rate, RR, QT, QTcF, refer to Section 8.4.2)
- Infection surveillance (refer to Section 10.2.3)
- Liver safety (ALT, AST, ALP, TBL, PT/INR, γGT levels, refer to Section 10.2.1)
- Hematology and blood chemistry parameters (refer to Section 8.4.1)
- Vital signs (refer to Section 8.4.4)
- Physical examination (refer to Section 8.4.7)
- AEs and SAEs recording (refer to Section 10)

Cohort B

Approximately 12 patients will be enrolled in Cohort B to ensure that at least 10 patients complete the study in this Cohort.

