The study consists of (refer to Figure 3-3):

• A screening period that lasts up to 60 days and consists of a screening visit and a run-in period.

Commercially Confidential Information

During the run-in period first morning void urine collection will be performed one time. It may be substituted by a 24h urine collection. A renal biopsy may be taken at any time during the run-in period as baseline, if the most recent biopsy is older than 3 months.

• A baseline period of about 30 days, made up by two visits. During this period baseline values for key complement biomarkers, as per objectives, and efficacy related proteinuria will be established. Patients during baseline should be under stable doses of supportive therapy (antihypertensive and antiproteinuric therapy, e.g., angiotensin converting enzyme inhibitors, angiotensin II receptor blockers, CCI as per KDIGO guidelines KDIGO 2012).

Commercially Confidential Information
Last baseline visit will be performed the day before dosing.

• Treatment period of 12 weeks CCI

• Follow-up period: A Commercially Confidential Information 12 weeks of safety follow-up without treatment. At the end of Treatment period if the Investigator does not deem it to be clinically beneficial for the patient to continue treatment, or if a patient does not want to continue treatment, the patient will enter the follow-up period. (refer to Figure 3-2).

Commercially Confidential Information

- A safety follow-up period up to 12 weeks with 3 outpatient visits on Days 113, 127 and 155

 Commercially Confidential Information
- An end of study visit scheduled on Day183

Commercially Confidential Information

The renal biopsy to be collected during run-in is mandatory in case the most recent bioptic material is older than 3 months. The renal biopsy to be collected at Week 12 is mandatory.

Patients will remain on their supportive therapy, i.e. ACEi and/or ARB or other antihypertensive therapy,

Commercially Confidential Information for the duration of the trial.

To be dosed patients must have been on stable therapy with an ACEi and/or ARB.

Commercially Confidential Information

During the treatment period, no change in medication is allowed except for safety reasons.

Commercially Confidential Information

Patients must receive vaccinations against *N. meningitidis*, *S. pneumoniae* and *H. influenzae* prior to first LNP023 dosing.

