5.1 Inclusion criteria

Subjects eligible for inclusion in this study must meet all of the following criteria:

Population for Cohort A

Approximately 15 C3G patients with native kidneys and with reduced serum C3 levels (male or female) will be enrolled in Cohort A to ensure that 12 patients complete the study in this cohort.

- 1. Written informed consent must be obtained before any assessment is performed.
- 2. Male and female patients 18 years old or older at screening visit
- 3. Patients must have C3G as confirmed by renal biopsy within twelve months prior to enrollment (confirmation by the Investigator is required).
- 4. C3G patients with reduced C3 at screening Commercially Confidential Information
- 5. Able to communicate well with the investigator, to understand and comply with the requirements of the study.
- 6. At screening and baseline visits, patients must weigh at least 35 kg to participate in the study, Commercially Confidential Information
- 7. Vital signs should be within the following ranges: body temperature between 35.0-37.5 °C systolic blood pressure, 80-170 mm Hg diastolic blood pressure, 50-105 mm Hg pulse rate, 45 100 bpm
- 8. Estimated GFR (using the CKD-EPI formula) ≥30 mL/min per 1.73 m² for patients on a maximum recommended or maximum tolerated dose of an angiotensin converting enzyme inhibitor (ACEI) or angiotensin receptor blocker (ARB).
- 9. UPCR \geq 100 mg/mmol sampled from first morning void (or \geq 1 g/24h total urinary protein excretion from a 24h collection during run-in) at run-in (Visit 20) or at baseline (Visit 30).
- 11. Prior to Day 1, all patients must have been on supportive care including a maximally tolerated dose of ACEi or ARB for at least 30 days.

- 12. Commercially Confidential Information
- 14. Commercially Confidential Information

Population for Cohort B

Approximately 12 C3G kidney transplanted patients (male or female) with C3G recurrence will be enrolled in Cohort B to ensure that at least 10 complete the study in this cohort.

- 16. Written informed consent must be obtained before any assessment is performed.
- 17. Male and female patients 18 years old or older at screening visit
- 18. Patients must have C3G recurrence after transplantation as confirmed by renal biopsy after transplantation within twelve months prior to enrollment (confirmation by the Investigator is required).
- 19. Able to communicate well with the investigator, to understand and comply with the requirements of the study.

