- 20. At screening and baseline visits, patients must weigh at least 35 kg to participate in the study, Commercially Confidential Information
- 21. Vital signs should be within the following ranges: body temperature between 35.0-37.5 °C systolic blood pressure, 80-170 mm Hg diastolic blood pressure, 50-105 mm Hg pulse rate, 45 - 100 bpm
- 22. Commercially Confidential Information
- 23. Normal or elevated urinary protein excretion at screening or at baseline (Visit 30).
- 25. Commercially Confidential Information
- 26. Commercially Confidential Information
- 27. No histological/laboratory/clinical signs of allorejection
- 28. If applicable, induction treatment after allotransplantation needs to be completed >30 days before screening visit.
- 29. Transplantation of a kidney allograft >90 days before screening visit
- 30. Patients need to be on a stable dose of immunsuppressive regimen CCI prior to Day 1. Any approved treatments are allowed for this purpose (if not prohibited as per protocol).
- 32. Commercially Confidential Information

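### The SAP's definitions of prior and concomitant medication leave out any drug started before Day 1 and continued past it

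*SAP*

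**What the plan says.** The Treatment paragraph of SAP Section 7.2 runs in this order. First comes the main commitment: "Concomitant medications and significant non-drug therapies prior to and after the start of the study treatment will be listed and summarized", by ATC class, preferred term and cohort. Next, the same two tables are promised for a set of medications of interest; that list is not visible in the public text. The paragraph closes with two definitions:

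- The rule for the concomitant class reads: "Concomitant medication is defined as any medication started on or after LNP023 treatment and ended/ongoing by Day 84".
- The rule for the earlier class, which sets both a start and an end condition, reads: "Prior medications are defined as any treatment started and ended before the first dose of LNP023 on Day 1".

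Protocol Section 12.3 makes the same main commitment and defines neither class.

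On background therapy, the protocol says:

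- Cohort A, inclusion criterion 11: before Day 1, "all patients must have been on supportive care including a maximally tolerated dose of ACEi or ARB for at least 30 days".
- Cohort B, Section 3 (Study design): "To be dosed patients must have been on stable therapy with an ACEi and/or ARB".
- Cohort B, inclusion criterion 30: "Patients need to be on a stable dose of immunsuppressive regimen" before Day 1.
- Both cohorts, Section 3: "Patients will remain on their supportive therapy, i.e. ACEi and/or ARB or other antihypertensive therapy", for the duration of the trial.
- Both cohorts, Section 3: "During the treatment period, no change in medication is allowed except for safety reasons".

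**The concern.** Both definitions turn on the start date, and together they do not cover the time line. A drug already in use when LNP023 begins, and not stopped, fails the test for prior because it has not ended. It fails the test for concomitant because it began too early.

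In many trials this would touch a few incidental drugs. Here it touches the therapy that the protocol requires. Antiproteinuric background treatment has to be in place before dosing and is kept on, and Cohort B enters on a stable immunosuppressive regimen. Because changes during treatment are barred except for safety, newly started drugs are the exception and continuing drugs the rule. The definition of concomitant captures the exception and misses the rule.

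Neither cohort has a control group. A reader weighing the Week 12 change in UPCR or in C3 Deposit Score will want to see what else patients were taking, and a summary table is where that reader will look. There is also a programming risk: one programmer may follow the definitions as written and another the usual meaning of concomitant, and they would produce different tables from the same paragraph.

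**Working it through.** The plan gives no figure to reproduce here, so the check is one of logic.

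**Inputs.** Let S be the start day and E the end day of a medication, with first dose on Day 1 and E unlimited if the drug is ongoing. The two rules come from the Treatment paragraph of SAP Section 7.2.

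- Prior: S < 1 and E < 1.
- Concomitant: S ≥ 1, and ended or ongoing by Day 84, which implies S ≤ 84.

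**A drug spanning Day 1** has S < 1 and E ≥ 1. The condition E ≥ 1 contradicts the rule for prior, and S < 1 contradicts the rule for concomitant. The result does not depend on how the Day 84 clause is read: whether a drug must have ended by Day 84 or may still be ongoing then, a spanning drug has already failed on its start date.

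**Patterns, as written and under the proposed rule.** The proposed rule is: concomitant if E ≥ 1 and S ≤ 84; prior unchanged.

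| Medication | SAP as written | Proposed rule |
|---|---|---|
| Started and ended before Day 1 | prior | prior |
| Started before Day 1, ended on Day 40 | neither | concomitant |
| Started before Day 1, still ongoing | neither | concomitant |
| Started on Day 1, ended on Day 40 | concomitant | concomitant |
| Started on Day 30, ongoing at Day 84 | concomitant | concomitant |

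Under the proposed rule every drug started by Day 84 falls in exactly one class. Either E < 1, which forces S < 1 and makes it prior, or E ≥ 1, which makes it concomitant.

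A drug first started after Day 84 is in neither class under both rules. That follows from a cutoff placed at Week 12 and is a separate matter from the gap at Day 1.

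**Does the protocol produce spanning drugs?**

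- ACEi/ARB, Cohort A: at least 30 days of use before Day 1 gives S < 1; remaining on supportive therapy gives E ≥ 1.
- ACEi/ARB, Cohort B: stable therapy before dosing gives S < 1; remaining on supportive therapy gives E ≥ 1.
- Immunosuppression, Cohort B: a stable regimen before Day 1 gives S < 1. E ≥ 1 follows from the bar on changes during treatment. Protocol Section 9.1.1 is consistent with this, since it speaks of raised doses of concomitant immunosuppression in the setting of graft rejection.

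All three fall in the rows marked neither.

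**Is the gap filled elsewhere?** Protocol Section 12.3 has no start or stop rule. Protocol Section 6.2.1 requires recording of drugs administered after enrolment, with start and discontinuation dates. It therefore supplies the data for a correct classification but not the classification itself.

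**The case against.** The strongest reply concerns scope. The definitions come after the medications-of-interest sentence and may govern only those added tables. The main ATC tables would then rest on the lead sentence alone, whose wording covers therapy both before and after the start of treatment, and background drugs could still appear there. This stands. A reader might infer that the trial's summary tables as a whole would fail to show background therapy; the documents do not support going that far. The reference to two tables suggests that the main summary is also split in two, but nothing says by which rule. If only the added tables are affected, the omission also depends on whether ACEi/ARB and immunosuppressants are on the list, which cannot be seen. The list being absent from the public text is not a fault in the plan.

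Second, a competent programmer would know what was intended. Perhaps, but that means departing from an explicit definition, and the purpose of a SAP definition is to make such judgement unnecessary.

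Third, little is lost. Concomitant therapies are also to be listed by subject, dates are collected, and ACEi/ARB use is a condition of entry or dosing, so the information can be recovered unless the listings are filtered by the same definitions. This stands as a limit on the consequence. A listing still does not deliver the summary that both documents promise.

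Fourth, sites might open a new medication record at Day 1, which would give a continuing drug a Day 1 start. The documents state no such convention, and it is a weak basis for a definition.

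**Conclusion.** The gap is real on the plain wording of two intact sentences, and it falls on therapy that the protocol expects to span Day 1. Whichever tables the definitions govern would, if programmed literally, omit continuing ACEi/ARB and continuing Cohort B immunosuppression, contrary to the stated aim of those summaries.

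The size is modest. Only descriptive tables in a non-confirmatory study are affected. A reader might take the point further, to missing medication data or to a flaw in the efficacy results. Neither follows: recording under Protocol Section 6.2.1 does not use these definitions, and neither do the MMRM for UPCR and the signed rank analysis of C3 Deposit Score in SAP Section 6.1.3. The number of patients affected cannot be derived, because the documents give no medication counts and no convention for start dates of continuing drugs.

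The conclusion assumes that the original start date of a continuing drug is kept in the database. If the definitions serve only the medications-of-interest tables, it also assumes that the drug classes concerned are on that list. The correction should be made before the tables are programmed.

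**What to change.** In the Treatment paragraph of SAP Section 7.2:

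1. Define concomitant medication as any medication taken on at least one day from the first dose of LNP023 through Day 84, whatever its start date. Adding a third class for drugs started before the first dose and continuing would close the gap equally well, and would show background therapy separately from new drugs.
2. Keep the definition of prior medication as it is.
3. State whether the main ATC tables, the medications-of-interest tables, or both use these definitions.

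The cost is one or two sentences and one derivation flag. Start and discontinuation dates are already collected under Protocol Section 6.2.1, so no new data and no protocol change are needed.

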6.1.3 Treatment arms/group

This is an open label study where approximately 15 patients enrolled into Cohort A and approximately 12 patients into Cohort B will be treated for up to 14 weeks CCI with LNP023CCI

Commercially Confidential Information

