12.3 Treatments

The Safety set will be used for the analyses below.

Categorical data will be summarized as frequencies and percentages. For continuous data, mean, standard deviation, median, 25th and 75th percentiles, minimum, and maximum will be presented.

Data for study drug administration will be listed by subject and summarized by treatment group. Summary includes:

• Number of subjects who took all the planned doses of LNP023

Concomitant medications and significant non-drug therapies prior to and after the start of the study treatment will be listed and summarized according to the Anatomical Therapeutic Chemical (ATC) classification system, for all subjects.

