12.5.2 Safety endpoints

For all safety analyses, the safety set will be used. All listings and tables will be presented by subject.

Safety summaries (tables, figures) include only data from the on-treatment period with the exception of baseline data which will also be summarized where appropriate (e.g. change from baseline summaries). In addition, a separate summary for death including on-treatment and post-treatment deaths will be provided. In particular, summary tables for adverse events (AEs) will summarize only on-treatment events, with a start date during the on-treatment period (treatment-emergent AEs).

The on-treatment period lasts from the date of first administration of study treatment to 30 days after the date of the last actual administration of any study treatment.

Adverse events

All information obtained on adverse events will be displayed by treatment group and patient.

The number (and percentage) of subjects with treatment emergent adverse events (events started after the first dose of study medication or events present prior to start of treatment but increased in severity based on preferred term) will be summarized in the following ways:

- by treatment, primary system organ class and preferred term.
- by treatment, primary system organ class, preferred term and maximum severity.
- by treatment, Standardized MedDRA Query (SMQ) and preferred term

Separate summaries will be provided for study medication related adverse events, death, serious adverse events, other significant adverse events leading to discontinuation and adverse events leading to dose adjustment.

A subject with multiple adverse events within a primary system organ class is only counted once towards the total of the primary system organ class.

Adverse events which will be counted for a specific treatment period are those which are treatment-emergent. These events are those with an onset after the start of the treatment period, or which were present prior to the start of the treatment period but increased in severity, changed from being not suspected to being suspected of study drug relationship, or developed into SAEs after the start of the treatment period.

Vital signs

All vital signs data will be listed by treatment group, patient, and visit/time and if ranges are available, abnormalities will be flagged.

Summary statistics will be provided by treatment and visit/time.

12-lead ECG

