**Cohort B** 

Approximately 12 C3G kidney transplanted subjects (male or female) with C3G recurrence subjects will be enrolled in Cohort B to ensure that at least 10 subjects complete the study in this Cohort.

Figure 1-3 depicts the study design of Cohort B, which consists of a screening period that lasts up to 60 days (made up by a screening visit and a run-in period), a baseline period of about 30 days (made up by two visits), a 12-week treatment period CCI , a safety follow-up period (Commercially Confidential Information 12 weeks of safety follow up) and the end-of-study (EOS) visit scheduled on Day 175.

Commercially Confidential Information

Follow-up period: A two-week down-taper of study medication and 12 weeks of safety followup without treatment. At the end of Treatment period 1 or 2, if the Investigator does not deem it to be clinically beneficial for the subject to continue treatment, or if a subject does not want to continue treatment, the subject will enter the follow-up period (refer to Figure 1-2).

Commercially Confidential Information

• A safety follow-up period up to 12 weeks with 3 outpatient visits on Days 113, 127 and 155 Commercially Confidential Information

An end of study visit scheduled on Day183 Commercially Confidential Information

Efficacy in terms of reversal of renal histopathologic changes will be assessed after the 12-week treatment period. Proteinuria and individual clinical response to various pharmacodynamic markers as well as pharmacokinetics will be assessed over the 12-week treatment period.

In this context, proteinuria will be assessed by collecting 24-h urine and first morning void urine to assess the change in and evolution of: UA and UP excretion, UACR and UPCR, creatinine clearance and hematuria.

Commercially Confidential Information

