#### Adverse events

All information obtained on adverse events will be displayed by run-in period, treatment period (i.e. dose-escalation phase, LNP023 200mg b.i.d., tapering down phase) and subject.

The number and percentage of subjects with adverse events will be tabulated by body system organ class (SOC) and preferred term (PT) with a breakdown by run-in and treatment period. A subject with multiple adverse events within a body system is only counted once towards the total of this body system and treatment period (including run-in period).

Summaries of SAEs will be provided in a similar manner.

Commercially Confidential Information

Further displays of AEs may be produced in order to appropriately describe the outcomes seen in this trial.

For the legal requirements of ClinicalTrials.gov and EudraCT, two required tables on treatment emergent adverse events which are not serious adverse events with an incidence greater than 5% and on treatment emergent serious adverse events and SAE suspected to be related to study treatment will be provided by system organ class and preferred term on the safety set population.

If for a same subject, several consecutive AEs (irrespective of study treatment causality, seriousness and severity) occurred with the same SOC and PT:

- a single occurrence will be counted if there is  $\leq 1$  day gap between the end date of the preceding AE and the start date of the consecutive AE
- more than one occurrence will be counted if there is > 1 day gap between the end date of the preceding AE and the start date of the consecutive AE.

For occurrence, the presence of at least one SAE / SAE suspected to be related to study treatment / non SAE has to be checked in a block e.g., among AE's in  $a \le 1$  day gap block, if at least one SAE is occurring, then one occurrence is calculated for that SAE.

The number of deaths resulting from SAEs suspected to be related to study treatment and SAEs irrespective of study treatment relationship will be provided by SOC and PT.

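### SAP 7.2 ends the concomitant-medication window at Day 84, so drugs newly started in the later taper or second treatment period enter no summary table

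*SAP*

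**What the plan says.** The Treatment part of SAP 7.2 first promises a listing: "Data for study drug administration and concomitant therapies will be listed by treatment group and subject". It then repeats the plan of protocol 12.3: "Concomitant medications and significant non-drug therapies prior to and after the start of the study treatment will be listed and summarized". Neither sentence gives an end day. After announcing further tables for medications of interest, the SAP gives two definitions: "Concomitant medication is defined as any medication started on or after LNP023 treatment and ended/ongoing by Day 84", and "Prior medications are defined as any treatment started and ended before the first dose of LNP023 on Day 1".

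Other windows in the plan run later than Day 84:

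- Protocol 12.5.2, for the safety summaries: "The on-treatment period lasts from the date of first administration of study treatment to 30 days after the date of the last actual administration".
- SAP 7.2, Adverse events: events are displayed by run-in period and by "treatment period (i.e. dose-escalation phase, LNP023 200mg b.i.d., tapering down phase".

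Dosing also runs later. Under protocol 6.1.3, patients in both cohorts "will be treated for up to 14 weeks" (text after this is blacked out). SAP 1.4 shows the taper for Cohort B: "A two-week down-taper of study medication and 12 weeks of safety followup". The same paragraph refers to the end of a first or a second treatment period. In both cohorts, the assessment schedules (protocol Tables 8-1 and 8-3) dispense study drug at Visit 190 (Day 85), Visit 195 (Day 169) and Visit 200 (Day 92 or 176).

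**The concern.** The medication rule closes while some patients are still taking LNP023, and before the adverse-event window closes. A drug newly started in the taper or in a second treatment period belongs to no category that the SAP summarises. An adverse event in the tapering-down phase would be tabulated, while a drug newly started to treat it would not.

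The summary tables, including those for medications of interest, would then understate therapy added after Day 84. A reader of the study report who took them as covering everything added on LNP023, as protocol 12.3 leads one to expect, would be misled about that stretch. What is at stake is the completeness of descriptive safety output.

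**Working it through.** **Inputs**

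- Concomitant: started on or after the first dose, and ended or ongoing by Day 84 (SAP 7.2).
- Prior: started and ended before Day 1 (SAP 7.2).
- Treatment period 12 weeks (protocol section 3); taper two weeks (SAP 1.4, visible for Cohort B only).
- Trough samples on Days 92 and 99, or 176 and 183 (protocol Table 2-1; SAP 1.3.2).
- On-treatment period: to last dose + 30 days (protocol 12.5.2).
- Completion for patients who roll over: Visit 190 (protocol 9.2), which is Day 85 in the schedules.

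**Step 1. Reproduce the stated duration.** 12 × 7 = 84 days; 84 + 14 = 98 days; 98 / 7 = 14 weeks. This matches the stated maximum of 14 weeks. Protocol 8.5.2 labels Days 92 and 99 as Weeks 13 and 14, so the last dose after one treatment period falls near Day 98 or 99. After a second period the corresponding day is about Day 183.

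**Step 2. Classify example drugs.** A drug can have ended or be ongoing by Day 84 only if it started on or before Day 84. The last column extends the window to last dose + 30 days, with the last dose taken as Day 99 (99 + 30 = Day 129).

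| Start day | Stop day | SAP rule | Window to Day 129 |
|---|---|---|---|
| -20 | -5 | prior | prior |
| 10 | 20 | concomitant | concomitant |
| 80 | 95 | concomitant | concomitant |
| 85 | 90 | neither | concomitant |
| 90 | 97 | neither | concomitant |
| 110 | 115 | neither | concomitant |

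The third row matters: a drug started by Day 84 and carried into the taper is counted. Only new starts after Day 84 are missed.

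**Step 3. Dosing days on which a new start is not counted**

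- Last dose near Day 99: (99 − 84) / 99 = 15 / 99 = 15%. With exactly 14 weeks, (98 − 84) / 98 = 14 / 98 = 14%.
- Last dose near Day 183: (183 − 84) / 183 = 99 / 183 = 54%.
- Roll-over at Day 85: 85 − 84 = 1 day in this study.

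**Step 4. The same against the on-treatment period**

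- Day 99 + 30 = Day 129: (129 − 84) / 129 = 45 / 129 = 35%.
- Day 183 + 30 = Day 213: (213 − 84) / 213 = 129 / 213 = 61%.

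Step 4 includes 30 days after the last dose, so Step 3 is the measure for drugs started while on LNP023. Both steps count calendar days. Neither estimates how many medications are missed.

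**The case against.** The strongest case on the other side has five parts.

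1. **The data are still listed.** The by-subject listing carries no stated Day 84 limit, and with about 15 and 12 patients it can be read in full. This stands: the loss is confined to the summary tables.
2. **The affected group may be small.** Patients who roll over at Visit 190 have about one uncovered day. The documents do not say how many will instead enter the taper or a second period, and text after the mention of Visit 190 in protocol 9.2 is blacked out. This stands as a limit on size.
3. **Few new drugs should start.** Protocol section 3 allows medication changes during the treatment period only for safety reasons. That limits numbers in a second treatment period. The sentence does not name the taper, though, and drugs started for safety reasons are ones a safety table should show.
4. **The cut may be deliberate.** Day 84 matches the Week 12 endpoint, and the definition follows a list of medications of interest that is not shown. It could have been meant for those tables or for a Week 12 view. The SAP does not say so, and an additional Day 84 table would serve that purpose.
5. **The last dose + 30 days window is stated for safety summaries.** Protocol 12.3 does not apply it to medication tables. This is correct. The case for it is consistency with the adverse-event window.

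Two stronger readings are tempting. A reader might infer from Step 3 that no concomitant medication at all is counted on those days. The rule does not work that way, because drugs started on Days 1 to 84 and continued remain counted. A reader might also infer that efficacy results are affected or that withdrawal effects are hidden. The models in SAP 6.1.3 and 6.2.3 do not use these tables, and the documents give no rate of relapse, rejection or withdrawal effects in the taper.

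**Conclusion.** The point holds in a limited form. Read literally, SAP 7.2 leaves a drug newly started after Day 84 in neither the concomitant nor the prior summary. That conflicts with protocol 12.3, which sets no end day, and with the SAP's own adverse-event displays, which include the tapering-down phase.

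The uncovered stretch is about 15 of 99 dosing days, or about 99 of 183 for a patient who completes a second treatment period and its taper. It applies to patients who do not roll over at Visit 190. No primary or secondary estimate changes.

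This rests on three assumptions: that the definition governs all the medication summaries, since no narrower scope is stated; that dosing ends near Day 99 or Day 183, as the visible schedule implies; and that the Cohort A taper, whose wording is blacked out, follows the same visit days as Cohort B. It is worth correcting because the summary tables would otherwise be incomplete and the correction is cheap.

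**What to change.** In the SAP 7.2 definition, replace the Day 84 end condition with the end of the protocol's on-treatment period: last dose + 30 days, or completion of this study if the patient rolls over earlier. The medication summaries then match the protocol's safety-summary window.

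If a Week 12 view is wanted for reading the primary endpoint, keep the Day 84 cut as an additional table labelled as such. It has a second use. For a patient whose last dose falls before Day 54, last dose + 30 days ends before Day 84 (54 + 30 = 84), so the new window would be shorter than the present one.

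Tabulating by phase is optional. If it is done, use the phases named in the SAP adverse-event section: run-in, dose escalation, 200 mg b.i.d. and tapering down. That section names no separate phase for a second treatment period.

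The cost is one SAP sentence, one changed date condition and possibly one extra table. No new data are needed: protocol 6.2.1 already requires medications to be recorded after enrolment, and the schedules carry the concomitant-medication row through follow-up.

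The change does not settle a neighbouring gap in the same definitions. Drugs started before Day 1 and still ongoing also meet neither definition and need their own correction.
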